### Ethical aspects

The ethical considerations and good clinical practices set out in the Code of Good Practice in Research of the Fundación de la Orden Hospitalaria San Juan de Dios, following the latest version of the Declaration of Helsinki (2013) and the Taipei Declaration (2016) regarding the custody of health databases, will be taken into account.

1. **Clinical Research Ethics Committee and/or Institutional Review Board.**  
Documented approval will be obtained from the Fundación San Juan de Dios.
2. **Patient information and consent.** Informed consent (IC) will be requested from all individuals who voluntarily participate in this study. Participants will be informed of the purpose and objectives of the study and the type of participation that will be requested of them, by means of a patient information sheet (HIP). The decision to withdraw from the project during the course of the project will be respected at all times. Consent to participate may be revoked at any time without any detriment to the participant.

**3. Confidentiality.** In accordance with Organic Law 3/2018, of 5 December, on Personal Data Protection and guarantee of digital rights (29), only data that are strictly necessary for the purposes of the study will be obtained. All information will be stored in a computerised archive with access limited to authorised study personnel, with a double password for research purposes. No data that could reveal the personal identity of the participating subjects will appear in any of the study reports.

The investigators undertake to preserve the confidentiality of the data as provided for in the Law on Patient Autonomy, Information and Clinical Documentation (Law 41/2002 of 14 November 2002) (30), and will inform patients that all data will be kept in computerised format and in a strictly confidential manner. All project investigators will ensure adherence to applicable personal data protection regulations. Data will be destroyed at the end of the study and only data necessary for the present research will be used.

All data will be stored in an anonymised form. The patient will be informed, via the HIP, that his or her answers will be anonymised.

The confidentiality and pseudo-anonymisation of the data obtained will be guaranteed by anonymisation through an alphanumeric code. A pseudo-anonymised database will be generated and collected on a technological platform that meets the highest security standards. Pseudo-anonymisation will be maintained in the exploitation of the data.

Any personally identifiable information will be securely stored by computerised methods in the participating centres and by the PI of the project.

## **Study subjects**

### **Target population**

The target population will be made up of people over 65 years of age referred from the Emergency Department of the Centro Asistencial Universitario de León (CAULE) with a confirmed diagnosis of hip fracture, who are going to undergo hip fracture surgery at the HSJD.

### **Eligibility criteria for the unexposed cohort (protective factor).**

Inclusion criteria:

- Patients referred from the Emergency Department of the Complejo Asistencial de León (CAULE), with confirmation of the medical diagnosis of hip fracture by means of anterior-posterior and lateral radiography.
- Be over 65 years of age.
- Ability to walk before the fracture with or without the aid of instruments or people.
- Have signed the informed consent to participate in the research project.
- With access to a smartphone mobile phone with the option of installing applications.

Exclusion criteria:

- Polytrauma patients will be excluded.
- Metastatic origin of the fracture.
- Periprosthetic fracture.
- Patients with cognitive impairment that makes it impossible for them to use the PPP and who are not accompanied by a responsible person during the recovery process.

Withdrawal criteria:

- Mortality at hospital discharge.
- Presentation of complications.
- Non-compliance with the therapeutic plan or assessment process.

**Eligibility criteria** for the exposed (retrospective) cohort.

Inclusion criteria:

- Patients referred from the Emergency Department of the Complejo Asistencial de León (CAULE), with confirmation of the medical diagnosis of hip fracture by means of antero-posterior and lateral radiography.
- Be over 65 years of age.
- Ability to walk before the fracture with or without the aid of instruments or people.

Exclusion criteria:

- Polytrauma patients will be excluded.
- Metastatic origin of the fracture
- Periprosthetic fracture.

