## METHODOLOGY

### Study design

Longitudinal analytical observational study of ambispective cohorts with two groups, an exposed cohort (retrospective) and a non-exposed cohort (protective factor), made up of people over 65 years of age referred from the Emergency Department of the University Care Centre of León (CAULE) to the Hospital San Juan de Dios de León (HSJD) with a confirmed diagnosis of hip fracture and who underwent hip fracture surgery in the latter during the years 2020 and 2021, and who will be followed up during the year after surgery, in the latter, to undergo hip fracture surgery during the years 2020 and 2021 and who will be followed up during the year following the surgery.

Two groups:

- Non-exposed cohort (protective factor): group of patients operated on during the year 2021 in HSJD for hip fracture and to which the new programme implementing functional recovery and therapeutic exercise will be applied with follow-up for one year. The implementation of a functional recovery plan and subsequent follow-up is considered a protective factor in relation to the loss of functionality.
- Exposed cohort (retrospective): complete cohort of patients operated on during the year 2020 in HSJD for hip fracture and to whom no specific functional recovery plan was applied.

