## Sampling

**Sample and procedure for inclusion of patients in the unexposed cohort.**

In order to carry out an analysis of the new care model (functional recovery programme and patient follow-up through a digital application), the entire simple universe will be included, a complete cohort analysis, with follow-up at 1, 3, 6 and 12 months using a digital toolFollow-up will be carried out at 6 weeks, 4 months and 12 after discharge according to the protocol of the orthogeriatrics unit.

The patient will be given instructions on how to download the application to their mobile device. The application is available in the open repository of mobile applications for public use. Once the app is installed, the patient will be provided with a personal access code that does not include recognisable personal data. This code will be used to connect to the therapeutic plan and to the questionnaires provided by the patient when registering with the Traumatology Service. Only the principal investigator (PI) will have a system of correlation between the code and the patient's personal data, be responsible for its safekeeping.

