#### **First group: variables established in the National Hip Fracture Registry, defined according to its protocol**

These scales will be administered to both groups:

- Cohort of unexposed patients: to be administered on the dates indicated.

- Cohort of exposed patients (retrospective): data will be retrieved from the Exceldata collection system that the medical management of the HSJD manages for the follow-up of these patients and the report to the national hip fracture registry.

These variables include socio-demographic, clinical and functional characteristics prior to surgery (Table I):

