**Table I: Sociodemographic, clinical and functional characteristics prior to surgery.**

Variables	Unit of measurement	Type
Age	Years	Independent quantitative
Genre	H- Male M- Female	Independent qualitative
Caregiver	1- Yes 2- No 3- Live alone	Independent qualitative
Preoperative mental assessment. Pfeiffer Test (SPMSQ-VE)	Points (0 to 10)	Qualitative
Mobility RNFC ladder	Levels (1 to 11)	Qualitative
Pre-fracture mobility. Gait assessment scale (mFAC).	Levels (0 to 6)	Qualitative
Side affected by the fracture	D- Law I- Left	Qualitative
Abbreviations: SPMSQ-VE: Short Portable Mental Status Questionnaire, (mFAC): Modified Functional Ambulatory Classificator, RNFC: Registro Nacional de Fractura de Cadera.		

- **Preoperative mental assessment. PfeifferTestor "Short Portable MentalStatusQuestionnaire" (SPMSQ-VE) (32)**

It assesses the patient's cognitive status at the time of administration. It consists of 10 questions that are asked prior to surgery, inwhich errors are computed. The test should be performed as close to the patient's baseline cognitive state as possible.

The inter- and intra-observer reliability of the SPMSQ-VE is 0.738 and 0.925 respectively, with an internal consistency value of 0.82 (32)

Pfeiffer test translated and validated in Spanish

1. What day is today? (Month, day, year).
2. What day of the week is today?
3. Where are we now?
4. What is your telephone number? (If no telephone, street address).
5. How old are you?
6. What is your date of birth?
7. Who is the current Prime Minister?
8. Who was the previous Prime Minister?
9. Tell me your mother's first surname.
10. Starting at 20, subtract 3 by 3 successively until you reach 0.

Errors are scored, 1 point per error. A score of three or more indicates cognitive impairment. If the educational level is low (elementary education), one more error is allowed for each category. If the level of education is high (university), one level less is allowed.

This scale is only administered prior to surgery to assess the patient's cognitive status.

This scale is administered on entry.

- **Pre-fracture mobility, according to the national fragility hip fracture registry(33).**

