This programme is divided into 5 phases, each of these phases coincides with a level of the gait assessment scale. Each individual will start at the level assigned by the doctor and will only have access to the videos of the indicated level and the levels below it. As the patient meets the recovery goals, the physician will provide access to the higher level videos. The functional recovery plan begins the day after the hip fracture and continues after the patient has been discharged for a total of 16 weeks.

- The therapeutic plan for the historical control group (standard practice until 31 December 2020) consisting of postural changes described in the standardised nursing care plan. Within this plan, the patient was moved to a sitting position prematurely (within the first 24 hours) and started to ambulate within the following 48

hours, provided that the patient's general condition allowed it. This group did not receive any specific functional recovery plan.

- The patient is discharged from hospital and will be assigned a link where he/she will be able to access the online platform to send information from the questionnaires sent during the established periods of 1, 3, 6 and 12 months and will also be sent videos illustrating the rehabilitation exercises that he/she will have to perform during this period. The patient and/or carer will be explained how the tool works, how to access the digital information content and how to access the questionnaires. A means of contact will be provided to resolve doubts, if any. The PI will have access through the web/app platform to a control panel where he/she will be able to detect a patient's lack of adherence, if any, or alerts related to clinical evolution, allowing for exhaustive monitoring of the patient.
- Analysis of results: The data collected will be analysed with the SPSS programme. The mean, median and standard deviation of each of the variables will be calculated. Based on the data obtained from the existing literature(31), having selected a sample of 67 patients, a normal distribution can be assumed for all variables  
For baseline demographic and clinical characteristics, a comparison of means for quantitative variables (t-Student), and of proportions (Chi-square) for qualitative will be performed  
The statistical analysis will be carried out with a confidence level of 95%, so that statistically significant values will be considered to be those whose probability is < 0.05.

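### Consent, smartphone access and a cognition-and-support exclusion filter only the 2021 cohort, and no adjustment of the comparison with 2020 is planned

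*Combined protocol and SAP*

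**What the plan says.** The protocol calls the 2021 programme patients the non-exposed or unexposed cohort and the 2020 historical controls the exposed cohort. I use the years.

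Both eligibility lists share three inclusion criteria (referral with radiographic confirmation, age over 65, walking before the fracture) and three exclusions (polytrauma, metastatic origin, periprosthetic fracture). Only the 2021 list adds:

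- "Have signed the informed consent to participate in the research project";
- "With access to a smartphone mobile phone with the option of installing applications";
- exclusion of "Patients with cognitive impairment that makes it impossible for them to use the PPP and who are not accompanied by a responsible person" in the recovery period. PPP is not defined; the Sampling and Data collection procedure sections suggest that the app is meant.

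The 2021 list alone also carries withdrawal criteria: death by discharge, complications, and non-compliance with the plan or the assessments.

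Study design describes the 2020 group as the "complete cohort of patients operated on during the year 2020 in HSJD for hip fracture", and its data come from the hospital's register return. The Overall objective and Hypothesis compare the two cohorts on return to pre-fracture function.

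The Analysis of results paragraph, under Description of the process, offers descriptive statistics, a 0.05 threshold and this: "For baseline demographic and clinical characteristics, a comparison of means for quantitative variables (t-Student), and of proportions (Chi-square) for qualitative will be performed". It names no between-cohort test of recovery and no adjustment, matching, weighting or restriction.

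**The concern.** A historical comparison can be read as a programme effect only if the two years' patients are comparable or their differences are handled. Here the protocol builds in a difference. The 2021 group is filtered on cognition, available support, access to technology and willingness to take part; the 2020 group is not. If the patients filtered out of 2021 have a different prospect of recovery, the cohorts would differ even if the programme did nothing. Justification of the Study describes a rural population living far from relatives and helpers, so selection on support is plausible here. The plan could show part of the imbalance and would correct none of it.

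**Working it through.** **1. Criteria side by side**

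| Criterion | 2021 | 2020 |
|---|---|---|
| Three core inclusions, three core exclusions | yes | yes |
| Signed consent | yes | not listed |
| Smartphone access | yes | not listed |
| Exclusion if impaired for the PPP and unaccompanied | yes | not listed |
| Withdrawal for death by discharge, complications, non-compliance | yes | not listed |

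The documents do not say whether withdrawn patients leave the analysis.

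**2. What the planned baseline tests can see**

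Table I, collected in both cohorts, holds age, sex, caregiver, Pfeiffer score and pre-fracture mobility. Tests on these may reveal imbalance in cognition and support. Smartphone access and willingness to consent are not in Table I, so selection on them stays invisible.

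**3. How large could the effect be?**

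The plan gives no figure to reproduce. Let p be recovery among all core-eligible patients, f the share failing the 2021-only criteria, and r the recovery rate in that share. With no programme effect:

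- recovery among those retained in 2021 = (p − f·r)/(1 − f);
- spurious difference from 2020 = f(p − r)/(1 − f).

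p = 50% is the background figure in the Introduction, which gives no time point. f and r have no source in the documents and are assumptions.

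| f | r | Calculation | Difference (points) |
|---|---|---|---|
| 10% | 40% | 0.10 × 0.10 / 0.90 | +1.1 |
| 20% | 20% | 0.20 × 0.30 / 0.80 | +7.5 |
| 30% | 40% | 0.30 × 0.10 / 0.70 | +4.3 |
| 30% | 20% | 0.30 × 0.30 / 0.70 | +12.9 |
| any | 50% | p − r = 0 | 0 |
| 10% | 60% | 0.10 × (−0.10) / 0.90 | −1.1 |
| 30% | 60% | 0.30 × (−0.10) / 0.70 | −4.3 |

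The +12.9 corner is demanding: it means 62.9% recovery in those retained against 20% in those excluded, a gap of about 43 points. If recovery at an early time point were 25% (assumed) and the excluded recovered at 10-20%, the range would be 0.10 × 0.05 / 0.90 = +0.6 to 0.30 × 0.15 / 0.70 = +6.4 points.

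**4. Can an adjusted model be supported?**

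Cohort, age, sex, Pfeiffer score, caregiver (yes/no) and an ordinal mobility score make six parameters. The only sample figure is 67, given in a sentence about normality that does not say whether it is the total or per group.

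| Recovery | 67 in total | 67 per group (134) |
|---|---|---|
| 50% | 33.5 / 6 = 5.6 events per parameter | 67 / 6 = 11.2 |
| 25% (assumed) | 16.75 / 6 = 2.8 | 33.5 / 6 = 5.6 |

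**5. Does a 2020 outcome exist?**

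Three places point in different directions:

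- The First group of variables says its scales apply to both cohorts, and the mobility scales there are scheduled up to one year.
- The Variables section says that follow-up previously ended after one month.
- The Second group, which includes follow-up mobility in Table II, is said to be measurable only in 2021.

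**The case against.** The best defence is that the filter is mild and belongs to the intervention. Data collection procedure lets a responsible person use the app for an impaired patient, and the phone criterion asks for access, not ownership. That stands: it lowers f and may make the bias small. It explains the 2021 criteria, but it does not justify an unfiltered comparator with no adjustment.

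Other replies carry less weight:

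- Ethical aspects requests consent from everyone who takes part voluntarily. Consent is still not a 2020 entry criterion, and those data come from a register.
- Limitations of the study names app use, the involvement of relatives and the lack of randomisation. It does not name the unequal criteria and gives no analytic remedy.
- Specific objectives includes an analysis of risk and protective factors, but no method or covariates are attached to it.

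A reader might infer that the Sampling section contradicts the eligibility list when it says of 2021 that "the entire simple universe will be included, a complete cohort analysis". The documents do not force that reading. Complete can mean every eligible patient, without sampling, and the same reading is needed for the 2020 cohort, which also has criteria.

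**Conclusion.** The concern holds. The two cohorts are selected by different rules, the difference bears on the main comparison, and nothing planned corrects it. This should be changed before the analysis, and the remedy is partial.

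Three stronger readings are tempting, and the documents do not support them:

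- **That the bias favours the programme, or has a known size.** Worse recovery in the excluded patients is a reasonable expectation, not a documented fact. The figures above rest wholly on assumed f and r, and they include zero and negative values.
- **That 67 is the total sample.** The text does not say, so the events per parameter are given both ways.
- **That 2021 would be measured 12 days later than 2020 (42 − 30).** Sampling counts 6 weeks from discharge. Variables gives no origin for the 2020 month and calls the 2021 visit one and a half months (45 − 30 = 15 days). The gap is unknown until the origins are established.

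**What to change.** 1. **Adjusted main analysis.** First establish which follow-up mobility data exist for 2020; without them no adjusted comparison of recovery is possible. Then pre-specify a model for return to pre-fracture function with cohort as the main term, adjusted for age, sex, Pfeiffer score, caregiver (yes/no) and pre-fracture mobility (registry levels 1-10, with level 11, unknown, set to missing). Use a penalised model or fewer covariates if events are few. Take the latest time point available in both cohorts. If that is about one month against 6 weeks, report the actual origins and gap, and say that the comparison covers an unfinished 16-week programme and does not answer the one-year objective. If an app-entered mobility value replaces a clinician-recorded one, state that the data source then differs by cohort.

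2. **Sensitivity analysis.** Apply one rule to both cohorts: exclude patients with three or more Pfeiffer errors (the protocol says "A score of three or more indicates cognitive impairment") and no caregiver in Table I. The protocol's correction for education needs a variable that is not in Table I. State that the rule only approximates the 2021 exclusion. It can remove eligible patients, and it can miss those who had a caregiver before surgery but were unaccompanied during recovery.

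3. **Counts.** Report how many core-eligible 2021 patients were lost to each 2021-only entry and withdrawal criterion.

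4. **Limitations.** State that the entry criteria differ and that selection by consent and smartphone access cannot be removed.

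**Cost.** Items 3 and 4 need a screening log and wording. Item 1 needs no new baseline data, but it needs a check of the 2020 records and loses precision if events are few. Item 2 shrinks both cohorts. Some selection remains whatever is done.

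### Withdrawal criteria apply to the 2021 programme cohort only, and the plan does not say whether withdrawn patients stay in the analysis

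*Combined protocol and SAP*

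**What the plan says.** Under the eligibility criteria for the unexposed cohort (the protocol's label for the 2021 programme patients), three withdrawal criteria follow the inclusion and exclusion lists: "Mortality at hospital discharge", "Presentation of complications" and "Non-compliance with the therapeutic plan or assessment process". Complications are given no type, severity or time window there, and non-compliance has no threshold. The criteria for the 2020 cohort stop after inclusion and exclusion.

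Both cohorts are described as complete. Study design calls the 2020 group the "complete cohort of patients operated on during the year 2020 in HSJD for hip fracture". The Sampling section says of the 2021 group that "the entire simple universe will be included, a complete cohort analysis".

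The programme "continues after the patient has been discharged for a total of 16 weeks", and the principal investigator has a control panel on which "he/she will be able to detect a patient's lack of adherence". Of the 2020 patients the work plan says: "This group did not receive any specific functional recovery plan". They did have a standardised nursing care plan.

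The analysis paragraph in the work plan covers descriptive statistics, t and chi-square tests for baseline characteristics, and the 0.05 level. It names no analysis set, no missing-data method and no rule for withdrawn patients.

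**The concern.** The overall objective is return to pre-fracture function, 2021 against 2020. A rule that removes patients after enrolment, in one cohort only and for reasons related to outcome, can create a difference where none exists. If patients with complications or poor compliance recover less often than the rest, dropping them from 2021 raises that cohort's recovery rate even when the programme does nothing.

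A second problem does not depend on the 2020 data. The events that trigger withdrawal are also results of the study. Prevention of falls and mortality at 30 days and one year are specific objectives, and the adverse-event catalogue (falls, pneumonia, new fractures, death and others) is collected up to one year. If a patient leaves at the first such event, these results are truncated by the events they count.

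**Working it through.** **Step 1: the sections side by side.**

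| Item | 2021 programme cohort | 2020 cohort |
|---|---|---|
| Withdrawal criteria | Three | None |
| Described as complete | Yes (Sampling) | Yes (Study design) |
| Rule for data of withdrawn patients | None | Not applicable |
| Documented follow-up | To one year | About one month (Variables) |

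If withdrawal means leaving the analysis, the eligibility section contradicts Sampling and truncates the outcomes named in the specific objectives and Table II. If it means only stopping the programme, there is no contradiction, but the plan does not say so.

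**Step 2: which criteria are one-sided.** The asymmetry is that no withdrawal rule is set for 2020. Complications and non-compliance therefore remove patients from 2021 alone. In-hospital deaths and missed assessments are less clear: 2020 patients with the same events also have no later score, so these criteria are one-sided only if such 2020 patients are counted, for example as not recovered.

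**Step 3: size, as an illustration.** The plan has no figure of its own to reproduce. Inputs:

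- True recovery p = 50% in both cohorts. The background section gives this figure without a time point; using it here is an assumption.
- Share withdrawn for complications or non-compliance, w, and recovery among them, r: not in the documents, so varied.
- 67 per cohort. The analysis paragraph mentions 67 patients without saying whether per cohort or in total, so this too is an assumption.
- Test: two-sided pooled two-proportion z-test at 0.05, rejection rate by exact binomial enumeration. The plan names no outcome test.
- Deaths and missed assessments are handled alike in both cohorts.

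Apparent recovery among retained 2021 patients = (p - w × r) / (1 - w). Observed 2020 recovery = p. The number retained is 67 × (1 - w), rounded.

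| w | r | Apparent 2021 recovery | Bias (points) | Retained v 2020 | False p < 0.05 |
|---|---|---|---|---|---|
| 5% | 30% | (0.50 - 0.015)/0.95 = 51.1% | +1.1 | 64 v 67 | 5.6% |
| 5% | 10% | (0.50 - 0.005)/0.95 = 52.1% | +2.1 | 64 v 67 | 6.1% |
| 20% | 10% | (0.50 - 0.02)/0.80 = 60.0% | +10.0 | 54 v 67 | 19.6% |
| 20% | 30% | (0.50 - 0.06)/0.80 = 55.0% | +5.0 | 54 v 67 | 8.5% |
| 20% | 50% | (0.50 - 0.10)/0.80 = 50.0% | 0 | 54 v 67 | 5.0% |
| 20% | 60% | (0.50 - 0.12)/0.80 = 47.5% | -2.5 | 54 v 67 | 5.9% |

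With nobody withdrawn (67 v 67) the same test rejects in 4.7% of cases.

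The 5% rows stand for early withdrawals, the only ones that can matter within the one month of follow-up documented for 2020. The 20% rows become relevant only if later 2020 data are retrieved, since the programme runs 16 weeks and follow-up one year.

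Cohort size changes the rejection rate but not the bias. At w = 20%, r = 10%, it is about 12% if 67 is the total (33 per cohort; 26 v 33) and about 48% if each cohort had 200 patients (assumed; 160 v 200).

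**The case against.** The strongest reply is that the plan never equates withdrawal with removal from the analysis. It promises complete cohorts, and collecting complications to one year makes sense only if patients with complications stay. The programme and its variables are described as routine practice, so withdrawn patients might still have visit data. This stands as far as it goes: the bias is conditional, not demonstrated. It does not settle the matter, because the complete-cohort sentence is about who is sampled and is silent on later withdrawals.

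It can also be said that the numbers are small where the documents support a comparison. That is right: within one month the bias is +1 to +2 points, and the larger figures need late 2020 data that are not documented, as well as assumed rates. The truncation of complications, falls and deaths within 2021 is unaffected by this.

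Three stronger readings should be resisted:

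- A reader might infer that non-compliance could not arise in 2020 because those patients had no plan. They had a nursing care plan and lacked only a specific functional recovery plan. What is missing is a withdrawal rule.
- A reader might take the limitations section as predicting poor adherence to the exercises. The adherence it lists concerns the application used for data collection, so it supports missed assessments only.
- A reader might treat complications as certainly unrecorded in 2020. The text introducing the second group of variables says these can be measured only in 2021, but Table II in that group also lists the two mobility scales assigned to both cohorts. What the 2020 records hold is therefore not settled.

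**Conclusion.** The point holds. The documents state a one-sided, outcome-related withdrawal rule, do not say how withdrawn patients are analysed, and list the same events as outcomes. Confidence in this is high.

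That the comparison would favour the programme is probable, with moderate confidence. It requires that withdrawn patients leave the analysis or are no longer assessed, and that they recover less often than the rest. The second condition is likely for complications and uncertain for non-compliance: patients who stop exercising because they are well would reverse the sign. A reader might infer that the plan is shown to inflate the programme's effect; the documents do not support that.

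Confidence in the size is low, because every rate, the cohort size and the test in the illustration are assumed. The matter still needs settling before analysis: it affects the overall objective, and outcomes that are no longer collected cannot be restored by adjustment.

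**What to change.** Reconcile the withdrawal criteria with the Sampling section and state one analysis set for both cohorts, for example: *All eligible enrolled patients are analysed in the cohort they entered, whatever their later complications, adherence or attendance. Data collection ends only at death or revoked consent.*

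Then:

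- Remove the three criteria as reasons to leave the analysis. Whether a patient continues the exercises remains a clinical decision.
- Define complications, and count complications and in-hospital deaths as outcomes.
- State one rule for deaths in the recovery outcome and apply it to both cohorts at time points where 2020 status is known; counting death as not recovered is one option.
- Report missing outcomes with reasons by cohort, with one sensitivity analysis.
- Label any compliers-only analysis as secondary.

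The cost is low: one paragraph in the analysis section and an edit to the eligibility section. The apparent programme effect may be smaller, and some outcomes will still be missing. Unless later 2020 data are retrieved, the between-cohort comparison remains documented only to about one month.
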